## 2. Substance Use Consumption

Because parents underestimate their teen's involvement with SU (Cantwell et al., 1997), including reporting lower frequency of drinking than their children (Velting et al., 1998), parents will not be questioned about their child's SU. Using peers as corroborators raises issues of confidentiality, and to the extent that it leads to aggregating children around SU may lead to unintentional harm (Dishion et al., 1999), thus peers will not be assessed. Several procedures will be employed to maximize the fidelity of teens' self-reported data. First, assurance of confidentiality is primary; teens self-reported substance use has been shown to be accurate and reliable when confidentiality is assured (Haley et al., 1983; Luepker et al., 1981; Needle et al., 1983, Pechacek et al., 1984). Second, prior to each follow-up assessment teens will be administered a breath alcohol test, as research has shown that a positive test for alcohol is related to underreporting of alcohol use (Sobell et al., 1979b). Patients who test positive will be rescheduled for another interview.

Timeline Follow-Back – Substance use (TLFB). Substance use will be assessed at each contact point using the Timeline Follow-back Interview (TLFB; Sobell et al., 1980; Sobell & Sobell, 1992, 1996). The TLFB is a widely-used research and clinical assessment tool with good reliability and validity for various groups of individuals with alcohol use problems. Alcohol and drug consumption information is collected using a calendar format with temporal cues (e.g., holidays, special occurrences) to assist in recall of days when alcohol and drugs were used. The TLFB will be conducted for the last 90 days at baseline, 3-month, and 6-month follow-ups. Data from the TLFB will be summarized to yield the following variables: total number of alcohol use/drug

use days, total days abstinent from alcohol/drugs, average number of drinks per drinking day, and latency to first drink/first drug use. We have experience using this measure with adolescents in both our MI grants.

Adolescent Drinking Questionnaire (ADQ). The ADQ (Jessor, Donovan & Costa, 1989) consists of 4 items that assess recent drinking frequency (days per month), quantity (drinks per occasion), frequency of high-volume drinking ( $\geq 5$  drinks per occasion), and frequency of intoxication (feeling "drunk" or "very, very high").

Drug Use Questionnaire. This measure used in both MI grants assesses the number of days in the past 30 days teens used nicotine, marijuana, cocaine, LSD, PCP, inhalants, etc. Internal consistency in our sample was .75 (alpha = .80 when inhalants was dropped). Test/retest for mean number of days each substance was used was .83 from 3 to 6 month follow-up and .94 from 6 to 12 month follow-up.

Parent Substance Use. Parents will report on the extent to which they use alcohol, marijuana, and other drugs, and if they report no current use of a substance, whether they have stopped using the substance because they had a problem with use of the substance in the past. This information will be used for feedback purposes during the FCU.

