## **5B. Participants**

A total of 120 families (20 in open trial, 100 in RCT) with children primarily in mid-adolescence (commonly considered ages 14-16 years old) but some in early (13 years old) adolescence (Steinberg, 1999) will be recruited and randomized to receive either IMI/FCU or SC. **Inclusion criteria** are: (1) the target child is between the ages of 13-16 at the start of the project and living at home with at least one parent/guardian, (2) the target child must be seen in Truancy Court and must screen in with a t- score of 70 or above on one of the DSM-oriented scales (internalizing or externalizing problems) on the Child Behavior Checklist (i.e. reach the clinical cut-off), (3) the child must report 6 or more incidences of substance use in the last 90 days, and (4) parental consent and child assent are obtained. **Exclusion criteria** are: (1) adolescent meets diagnostic criteria for substance dependence suggesting need for more intensive services, and (2) the family is not able to speak and understand English or Spanish well enough to complete study procedures.

**Ethnic and gender considerations.** We expect to have approximately 60% to 70% boys in this sample. We will over-sample girls to lower the ratio of boys to girls. The ethnic racial distribution of Truancy Court is approximately 60% minority families, most of these being of Hispanic and low income status.

**Sample size projections.** Recruitment will take place in months 4 - 28. The RI Truancy Court has a current active roster of over 2,000 adolescents. In our pilot, we have worked with only one of the 4 magistrates in only 3 schools. If we consent approximately one-half of the referrals (in our pilot we have consented slightly more than half of referrals to date), baseline evaluations will easily be completed with about 100 families. This projection allows a 20% drop-out rate by 6 month follow-up ( $100 \times .8 = 80$ ).

**Piloting.** The PI, Co-I and treatment provider hired to conduct this study will each pilot 5-8 additional families at the start of this study. Final changes in the IMI/FCU will be made after these additional 20 families are piloted. Particular emphasis will be placed on adapting the school performance/attendance and sexual risk taking sections of both the individual and family motivational interventions.

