**5B1. Procedure.** Parent(s) or legal guardian(s) (hereafter referred to as "parents") of adolescents in the targeted age range will be recruited from the RI Truancy Court Program (see letters of support). Following arraignment procedures, families will be given information about the project by study staff who will be present at all truancy court arraignments and who will also answer any questions parents may have. Interested participants will be contacted by study staff at their second Truancy Court arraignment appointment. During this meeting, they will receive an oral and written description of the study, including a description of the project procedures, number of appointments and compensation for participation, potential risks and benefits, and confidentiality. Families who provide parental consent and adolescent assent will be administered the screening battery. If the child does not meet the substance use and CBCL inclusion criteria, they will be given a package of educational materials regarding truancy and SU.

**Assignment of participants to conditions.** In the open trial portion, the first 20 families will receive the IMI/FCU in order to inform adaptations to the current protocol and to examine its feasibility and acceptance. After this open trial, 100 families will be recruited and randomized into either the experimental or the comparison control condition. These assignments will be made soon after completing the baseline assessment and through random assignment using the urn method (Stout et al., 1994). Urn randomization assigns participants in a given subgroup to intervention conditions, but systematically biases the randomization in favor of balance among the intervention conditions. Participants will be randomized according to gender, substance abuse (yes or no), and meeting CBCL cut-off for internalizing only versus externalizing only or externalizing/internalizing.

**5B2. Baseline and follow-up assessments (IMI/FCU and PE).** Parents and teens will complete the

assessment battery described below at their local school. In person follow-up assessments will be held at 3 and 6 months following the baseline assessment. An RA who will be blind to condition assignment will conduct each follow-up assessment. The follow-up assessment battery will be identical to baseline.

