**Table 1. Timeline for assessment and intervention activities**

Design	Week 0	Week 1	Week 13	Week 25
	Baseline incl. video assess.	In person mtg.	3-month FU + Booster	6-month FU
IMI/FCU	X	feedback	X	X
PE	X a	education	X	X

Note. IMI/FCU = Individual MI/Family Check-Up ; PE = Psychoeducation.

aTwo video tasks only.

**Compensation for participation.** Parents and teenagers will each be compensated \$75 for the time it takes to complete baseline and \$75 for follow-ups.

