In the final phase of the intervention, the adolescent and counselor will collaborate to develop a plan for the future. This will include identifying goals for behavior change, exploring barriers to these changes, and providing strategic advice. A "goals sheet," which contains a variety of SU moderation goals, and harm reduction goals as well as some blank spaces for filling in other goals, including school attendance and performance, will be used here. Adolescents will be asked to select the preprinted goals that they would like to attempt and to generate other goals. This phase of the intervention was designed based on several research findings: first, that motivation is enhanced by encouraging participation in all decision-making regarding SU (Cooney et al., 1995), that using individualized strategies leads to more positive outcomes (Miller & Hester, 1986), and that most people prefer to select their own goals rather than having goals set for them (Sobell et al., 1993). Finally, it provides the opportunity for the counselor to support the adolescents' self-efficacy about making changes. At the completion of the session the counselor will provide the personalized feedback, the goals sheet, and informational handouts about SU to participants. In this adaptation, we expect the MI session takes about 90 minutes, spent over 2 sessions. The IMI covers the three constructs - intentions to use, normative beliefs about peer use, and attitudes towards peer use which have been shown to have the most consistent overall effects on adolescent SU (Stephens et al., 2009) as well as motivation to abstain which as been shown to have specific effects on marijuana use (King et al, 2009).

Family Check-Up (FCU). The FCU begins with using self-report assessments and the family videotape (FAsTask). The Research Assistant administers the self-report measures. The Treatment Providers administer the FAsTask in order to keep the RA who conducts the follow-ups blind to treatment condition as well as to observe the family interactions firsthand through a one-way mirror to assist in the feedback session.

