Parent Feedback Session (FCU). The primary component of the FCU is feedback about the assessment (self-report and video) obtained at baseline. The measures provide data which are incorporated into the feedback given to the parents along with the FAsTask data ([see Appendix 5](#)) for how measures are tied into the FCU feedback for parents). A week after the family completes the baseline assessment including FAsTask, parents will participate in their feedback session (i.e., the FCU). In our current study, for families referred from the Emergency Department (ED), 20% never returned for the first family assessment session to complete the FAsTask. (**Note:** We do not anticipate this to be a substantial problem in this application because there is frequent contact between families and the Truancy Court compared to one time contact with the ED.) Nonetheless, of the 79 families randomized to the FCU who completed the FAsTask, 77 returned for the feedback sessions of the FCU. All of these sessions will be audiotaped to evaluate fidelity. The session, which is based on MI techniques (Miller & Rollnick, 2002), is designed to support appropriate parenting and provide motivation to change maladaptive parenting (Dishion & Kavanagh, 2003). The FCU supports the parents in limit setting and also addresses the parent/adolescent relationship, parental understanding of the autonomy needs of the adolescent and greater involvement in the peer activities of the adolescent (Dishion et al., 1996a). The principles and techniques utilized in the parent session are based on techniques with demonstrated effectiveness in engaging families and motivating them to change. These include approaching the change process collaboratively (Patterson & Chamberlain, 1994), sharing assessment results with parents to build collaboration (Sanders & Lawton, 1993), providing a flexible menu of resources in the community (Dishion & Owen, 2002) and supporting motivation to change.

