### **4. Other Problem Behaviors**

Child Behavior Checklist. See description under Screening Measures (above).

Reckless Behavior Questionnaire (Shaw et al., 1992) is 10 items that assess how often the adolescent engaged in a variety of risk-taking behaviors and selected items from the Adolescent Health Behavior Questionnaire (Jessor et al., 1980) will be used to assess risky sexual behavior.

School Attendance TLFB. Incidences of cutting classes and skipping school will be assessed at each contact point using the Timeline Follow-back Interview (TLFB; Sobell et al., 1980; Sobell & Sobell, 1992, 1996). The procedures for collecting information regarding school truancy will be similar to the ones used on the TLFB for substance use. These procedures will not only allow us to collect data on school truancy but will also allow us to examine the co-occurrence of SU and school truancy. Similar to the TLFB for substance use, information will be collected for the last 90 days at baseline, 3-month, and 6-month follow-ups.

Truancy and Academic Performance. With permission from both school personnel and parents, data on truant behavior and grade point average will also be obtained for each student from school records provided by the school office personnel. These procedures have been successfully implemented in previous school-based studies examining school performance (Zimmerman et al., 2002).

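### The 3-month 90-day look-back opens about six days before the Week 1 session: this dilutes 3-month day counts by about 7%, and latency to first use by more if its clock starts there

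*Combined protocol and SAP*

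**What the plan says.** Section 5B2 sets the follow-up clock: "In person follow-up assessments will be held at 3 and 6 months following the baseline assessment". Table 1 puts baseline at Week 0, the in-person meeting (feedback or education) at Week 1, the visit labelled "3-month FU + Booster" at Week 13 and the 6-month visit at Week 25. Under 5C1, the parent session follows baseline by about a week: "A week after the family completes the baseline assessment including FAsTask, parents will participate in their feedback session". For the adolescent interview, "we expect the MI session takes about 90 minutes, spent over 2 sessions"; the date of the second session is not given. On randomization, 5B1 says: "These assignments will be made soon after completing the baseline assessment".

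Under Substance Use Consumption in section 5D, "The TLFB will be conducted for the last 90 days at baseline, 3-month, and 6-month follow-ups". The variables listed from the Timeline Follow-Back (TLFB) are use days, abstinent days, drinks per drinking day and latency to first drink or first drug use. No start point is given for latency. The School Attendance TLFB follows the same pattern: "information will be collected for the last 90 days at baseline, 3-month, and 6-month follow-ups". The Drug Use Questionnaire, by contrast, asks about the past 30 days.

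The entry rule in 5B is that "the child must report 6 or more incidences of substance use in the last 90 days". Section 5e makes between-group effect sizes the primary emphasis. Section 5f gives the percentage endorsing marijuana use at follow-up as an example of a proportion to be compared, without naming its instrument or window.

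**The concern.** The look-back is nearly as long as the interval from baseline to the 3-month visit, while the sessions start a week into that interval. The window therefore opens before either arm has had its feedback or education session, and nothing in the plan sets those days aside. Randomized arms should use at about the same rate in that gap, so including it adds no contrast and moves the arms together.

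The damage depends on the variable. A count of days loses only the share of the window that the gap occupies. Latency can be fixed by a single early event: a teen who uses on day 3 and abstains from the first session onward has a latency of 3 days if the clock starts at baseline. The 3-month effect sizes are meant to inform the size of a later trial (5e and 5f), so a diluted estimate carries forward.

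**Working it through.** **Plan's own figure.** Table 3 gives power .60 for d = .50 with 40 per group, and 63 per group for 80% power. A two-sided 5% comparison of two means gives power .609 (normal) or .598 (noncentral t), and 63 per group. Both reproduce.

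**Window.** Week 13 is day 13 × 7 = 91, so a 90-day look-back covers days 1 to 90. The session is at day 7. The days before it are 1 to 6, and 6/90 = 6.7%.

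**Day counts.** If the effect starts at the session, d = .50 × (1 − 6/90) = .467. Power with 40 per group falls to .551 (normal) or .540 (t), and 80% power needs 73 per group. With 5 or 7 pre-session days, d is .472 or .461.

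If the second interview session fell a week after the first (an assumption), 13 days would precede completion: 13/90 = 14.4% and d = .428. That is an upper case, because it credits no effect to the first session.

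**Chance of a first use in the gap.** Assume a constant rate of u uses per 90 days. With at most one use per day and independent days, the chance is 1 − (1 − u/90)^6. In Poisson form it is 1 − exp(−6u/90).

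| Uses per 90 days | Independent days | Poisson |
|---|---|---|
| 6 (entry minimum) | .339 | .330 |
| 10 | .507 | .487 |
| 20 | .779 | .736 |

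In Poisson form the chance passes one half at 90 × ln 2 / 6 = 10.4 uses per 90 days. The entry rule pools substances while latency is split into first drink and first drug use. A teen with 3 drinking days and 3 drug days has 1 − (1 − 3/90)^6 = .18 for each. The documents give no mean rate of use.

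**Any-use, only if derived from this TLFB.** Suppose true post-session any-use is 70% in PE and 45.6% in IMI/FCU (h = .50), and use in the gap (probability .33) is independent of later abstinence. The recorded rates become:

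- PE: 1 − .30 × .67 = .799
- IMI/FCU: 1 − .544 × .67 = .635

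That gives h = .367, and the sample size for 80% power rises from 63 to 117 per group. The 70% and the independence are both assumptions.

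**6-month window.** Under Table 1, Week 25 is day 175. The look-back is days 85 to 174, which repeats days 85 to 90 of the 3-month window, all before the Week 13 booster. Under 5B2, 6 months is about day 182. The look-back is then days 92 to 181, with no overlap. On either reading the 6-month window lies wholly after the Week 1 session.

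**The case against.** A reader might infer that latency and any-use at 3 months mostly record use before the intervention. The documents do not support that. Only 6.7% of the window precedes the session, and at the one rate the plan states about two thirds of teens would have no use in the gap. A majority needs roughly 10 or more uses per 90 days. That is plausible, since 6 is a minimum, but it is not documented.

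Other points stand in whole or in part:

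- Any-use is not a listed TLFB variable. If it comes from the 30-day questionnaire, the 3-month value lies entirely after the first session.
- The any-use illustration probably overstates the loss. At a constant 6 uses per 90 days, the chance of some use in the other 84 days is 1 − (84/90)^84 = 99.7%. An assumed 70% therefore implies that some teens stop, and they are likely to be the lighter users, with less use in the gap. Clustered use also lowers the share affected.
- The latency origin is undefined. Dilution follows only if the clock starts at baseline or at the window start.
- Section 5C1 treats the baseline assessment and family video task as the start of the Family Check-Up. Similar use in both arms during days 1 to 6 is therefore an expectation, not a certainty.
- A 3-month interview on day 97 or later removes the gap, since 97 − 90 = 7.
- With 40 per group, the 95% interval on d is about ±1.96 × √(2/40) = ±.44, far wider than the .03 lost on day counts. The plan also admits that its effect sizes are unstable.
- Counting from baseline, close to assignment, is a legitimate intention-to-treat window.

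These points limit the size of the problem. They do not remove the pre-session days, and they leave two definitions open.

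**Conclusion.** The point holds in a limited form. On the nominal schedule about 6 of the 90 days in the 3-month window precede the Week 1 session, and no section excludes them. The expected loss is about 7% for day counts (d .50 to about .47). It is larger for latency if that is clocked from baseline or the window start: about one third of teens at the entry minimum would have their value set before the session, fewer for any one substance and more among heavier users. Any-use is at risk only if it is taken from the 90-day calendar.

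This rests on visits held on schedule, a constant use rate, similar pre-session use in the two arms, and effects that begin at the session. At 6 months no pre-session days are included; there is only a possible six-day double count, which depends on whether the visit is at Week 25 or at a full 6 months. This is a cheap improvement to the derivation of outcomes, not a flaw that invalidates the trial.

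**What to change.** Keep the 90-day interview and change the derivation:

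1. Take 3-month use days and abstinent days (as a proportion of days observed), latency, truancy and any TLFB-based any-use from one fixed calendar landmark just after the scheduled Week 1 session, for example day 8, up to the interview. Start the latency clock there.
2. Use the same landmark in both arms, not each family's actual session date, so that the comparison stays as randomized.
3. State the instrument and window for the percentage endorsing use.
4. Start the 6-month window the day after the 3-month interview so that no day counts twice, and reconcile Week 25 in Table 1 with the 6 months in 5B2.
5. Keep the baseline-origin version as a sensitivity analysis.

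The cost is a few lines in sections 5D and 5e. The TLFB is already a daily calendar, so on-schedule visits need no new data. The 3-month window shortens from 90 to 90 − 7 = 83 days. A later landmark such as day 15 would also discard a week in which an early effect could appear. If an interview is late enough that its look-back no longer reaches the landmark, the plan should say how the uncovered days are handled.

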## **5e. Data Analysis Plan**

First, all forms will be checked for any missing data following interviews and prior to data entry. All data will be entered into the project computer twice using double entry. Back-up copies of data will be made on a regular basis, and copies of data will be kept on a server to avoid accidental loss. Attrition effects will be evaluated by testing whether systematic differences exist between those participants who complete the research versus those who drop out. We will initially inspect distributions for outliers and deviations from normality and will perform the necessary modifications to adjust for these issues. We will also examine any pre-existing differences between the two conditions in demographic composition and all measures collected at baseline. Pre-existing group differences in these variables will be controlled in subsequent analyses, using baseline scores as covariates. While both parents can participate in the intervention, we will use the assessment of the primary caretaker in all data analyses. On outcomes such as parental monitoring we expect to find discrepancies between child and parent report; thus, all analyses will be conducted separately for parent and child. With data from only 80 subjects (40 per group) in intent-to-treat analyses, our primary emphasis will be on calculating effect sizes for between group differences.

Sample representativeness and data imputation. Following Little and Rubin (1987) and Diggle and Kenward (1994), we distinguish between completely random drop-outs (independent of phenotype or covariate, MCAR), random drop-out (drop-out may depend upon past measures, but is not dependent on what the measure would have been at the time of missed assessment, MAR) and informative drop-out (may depend on prior variables and on state at possible time of missed assignment). We are concerned with informative drop out. If necessary, standard methods of multiple imputation (Little, 2002; Schafer, 1997) will be used for variables where unplanned missingness is an issue. For each time point, we will conduct analyses to identify systematic biases that may have arisen through non-participation (non-random dropout).

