**Aim 1.** Treatment manual development does not require statistical analyses. The research team will meet with the PI at the beginning of the project, at the end of the open trial and end of the RCT to review the manual and suggest adaptations. With regard to feasibility, the following information will be calculated: refusal and enrollment rates, average number of days to intervention completion, and withdrawal rates of enrolled families. Acceptability will be examined by calculating percentage of "agree" or "strongly agree" answers on the SEF, with 80% set as an acceptable criterion. Treatment provider ratings conducted at post-intervention will also be calculated to determine clinician acceptability. Open-ended question responses at post-intervention and at completion of the follow-up assessment will also be qualitatively reviewed.

**Aims 2 - 4.** The domains to be analyzed, outlined in Table 2, include substance use (Aim 2), other problems (school, risky sexual behavior, Aim 3), and potential mediating processes including family management (Aim 4a), peer influences (Aim 4b) and teen cognitions (Aim 4c). The basic analytic strategy entails latent growth modeling to assess change in outcomes over time. This model allows for the inclusion of both categorical and continuous independent variables and for appropriate modeling of covariance structures when observations are correlated over time. Each teen and family outcome will be entered as a dependent variable in separate analyses with intervention condition serving as the primary independent variable. Appropriate time invariant covariates (e.g., age, sex, etc.) will be included as determined by preliminary analyses described above. Substance use in general, and marijuana use in particular, at baseline will be co-varied in one analysis to determine if there are any differential effects of the interventions by prior substance use. Post-hoc power analyses will be conducted using the beta weight and standard error of the estimate for intervention group to determine the number of subjects necessary for the given differences in outcomes to be significant in future studies. Measures of association (adjusted mean differences) and 95% confidence intervals will also be calculated to assess the effect size of the IMI/FCU.

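### Two Aim 2 timeline variables have no ordinary value for an abstinent teen (drinks per drinking day is undefined, latency to first use is censored), yet the plan gives them the same growth models as every other outcome and no rule for these cases

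*Combined protocol and SAP*

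**What the plan says.** The Timeline Follow-Back (TLFB) entry in section 5D, Substance Use Consumption, sets the window: "The TLFB will be conducted for the last 90 days at baseline, 3-month, and 6-month follow-ups". It then lists the derived variables: counts of days of use, "use days, total days abstinent from alcohol/drugs", and "average number of drinks per drinking day, and latency to first drink/first drug use".

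Section 5e assigns substance use to Aim 2 and states one approach for all domains: "The basic analytic strategy entails latent growth modeling to assess change in outcomes over time". It adds: "Each teen and family outcome will be entered as a dependent variable in separate analyses". Effect sizes are also to be estimated at each assessment. No outcome is exempted.

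Two general clauses in section 5e come closest to the problem. One promises unspecified adjustments after outliers and non-normal distributions have been inspected. The other says that multiple imputation, if needed, "will be used for variables where unplanned missingness is an issue".

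Eligibility in section 5B concerns any substance: "the child must report 6 or more incidences of substance use in the last 90 days". Drinking is not required.

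The documents give no value for drinks per drinking day when there are no drinking days. They give no time origin or censoring rule for latency, and no survival or two-part model.

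**The concern.** Both variables depend on what the teen does after randomization. Drinks per drinking day is a ratio whose denominator is zero for an abstainer. Latency has no event time for a teen who does not use in the window; all that is known is that it exceeds the window.

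Neither general clause covers this. An undefined ratio and a censored time are not departures from normality. An abstainer who completed the interview has no missing answer. Imputation would assign drinking to a teen known not to have drunk, and a likelihood-based growth model does the same implicitly when the cell is left blank. In a simple per-assessment comparison the teen drops out.

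Less use is the intended effect, so teens without a value should be more common in the IMI/FCU arm. A comparison among those who continue to use is then no longer protected by randomization. Section 5e puts its main emphasis on effect sizes, which are to inform the sample size of a later trial, so a distorted effect size damages the study's main product.

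There is a second source of undefined values. A marijuana-only teen can have no drinks per drinking day at baseline, in either arm. The baseline point of the growth curve is then absent for reasons unrelated to treatment.

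**Working it through.** **Inputs from the documents**
- 40 analysed per arm (section 5e)
- 90-day windows (section 5D)
- 5% level, and power .60 at d = .50 (section 5f, Table 3)
- Prior effects on marijuana use of h = .61 at 3 months and .46 at 6 months, against IMI alone (section 5f)

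The documents give no abstinence rates, drinks-per-day distribution or latency data. Those inputs below are assumptions.

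**1. The plan's own figure.** Two-sided power for d = .50 with 40 per arm is .609 by the normal approximation and .598 by the noncentral t. The stated .60 reproduces.

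**2. Drinks per drinking day, by hand.** Assume PE has 20 teens at 2 drinks and 20 at 6 drinks per drinking day, each with 10 drinking days. Assume IMI/FCU is identical, except that 12 of the lighter drinkers become abstinent.

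| Summary | PE | IMI/FCU |
|---|---|---|
| Drinkers only | (20×2 + 20×6)/40 = 4.00 | (8×2 + 20×6)/28 = 4.86 |
| Abstainers as 0 | 4.00 | 136/40 = 3.40 |
| Drinking days | 10 | 28×10/40 = 7 |
| Total drinks | 40 | 1,360/40 = 34 |

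The drinkers-only contrast has the wrong sign. The three all-teen summaries have the right one.

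The result depends on who abstains (PE stays at 4.00):
- 4, 8, 12 or 16 lighter drinkers abstain: IMI/FCU drinkers-only mean 4.22, 4.50, 4.86 or 5.33 (reversed)
- 6 lighter and 6 heavier abstain: 4.00 (hidden)
- 4, 8 or 12 heavier drinkers abstain: 3.78, 3.50 or 3.14 (sign correct)

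**3. The same variable with a smooth distribution.** Simulation, 400,000 per arm:
- Quantity = 1 + gamma(shape 2, scale 1.6), with no effect on quantity among continuing drinkers.
- Abstinence 25% in PE and 45% in IMI/FCU, that is h = 2·arcsin(√.45) − 2·arcsin(√.25) = .42.
- The log-odds of abstaining fall by 1 per SD of quantity.

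Drinkers-only means are 4.56 (PE) and 4.96 (IMI/FCU), d about .16 against IMI/FCU. With abstainers as 0 they are 3.42 and 2.72, d about .24 in favour.

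With weaker selection the drinkers-only d against IMI/FCU is about .1 (slope halved), .05 (quartered) and 0 (no selection). If heavier drinkers are likelier to abstain (slope −.5), it is .09 in favour. With about 30 and 22 drinkers left, the standard error of d is about √(1/30 + 1/22) = .28.

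**4. Loss of precision if only drinkers are compared.** Power = Φ(.5/√(1/n₀ + 1/n₁) − 1.96), assuming PE abstinence of 10% to 40% and an abstinence difference of h = .46 to .61 (the marijuana figures, borrowed).
- Best case: 36 and 29 drinkers, power .52.
- Worst case: 24 and 12 drinkers, power .29.

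With all 40 per arm, the same formula gives .61.

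**5. Latency.** Assume exponential times, with a proportion S abstinent at 90 days. Then λ = −ln(S)/90, the restricted mean is (1 − S)/λ, and the users-only mean is (restricted mean − 90S)/(1 − S).

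| | PE, S = .20 | IMI/FCU, S = .417 | Difference |
|---|---|---|---|
| Restricted mean to day 90 | 44.7 | 60.0 | 15.3 |
| Users only | 33.4 | 38.5 | 5.1 |

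At S = .25 and .45 the restricted means are 48.7 and 62.0 (difference 13.3), and the users-only means are 34.9 and 39.1 (difference 4.2). In both cases the effect shrinks to about a third and keeps its sign.

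**The case against.** The strongest reply is that the plan is silent, not wrong. A reader might infer that it removes abstinent teens from the comparison. The text does not say so. Coding an abstainer as 0, or latency as 90 days, would also fit the wording, and a likelihood-based growth model would keep a teen who has earlier drinking data. That stands: the distortion is conditional on how these values are handled. What remains is that no rule is given, and that the obvious defaults (leave blank, or impute) are the harmful ones.

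A reader might also infer that abstinence success generally reverses the comparison for both variables. The documents give no figures to support that. For drinks per drinking day, reversal needs abstinence concentrated in lighter drinkers, and the simulated reversal of .16 is smaller than its standard error at this sample size. For latency, both exponential examples are attenuated. A reversal can be built from a contrived two-point pattern: PE with 20 teens at day 10 and 20 at day 60, mean 35.0, and IMI/FCU with 12 of the late starters abstinent, users-only mean (20×10 + 8×60)/28 = 24.3. Nothing in the documents points to that pattern.

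The damage is also limited. Use days and days abstinent are defined for every assessed teen, and an abstinence benefit would show there. Section 5f uses days of marijuana use and percent using as its examples, not the two variables at issue. This stands, but no TLFB variable is named as the main one, so nothing directs a reader to the sound ones if results conflict.

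**Conclusion.** The point holds in conditional form. Drinks per drinking day is undefined for a teen without drinking days, and latency is censored for a teen without use in the window. The plan sends both through the same models as every other outcome and states no rule for either. For latency this is more than missing detail: a growth model for a repeated continuous measure does not suit a censored time, and a better method is available from the same data.

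If the values are left missing or imputed as ordinary missing data, the latency effect falls to about a third of its size in the exponential examples. An effect on drinks per drinking day can be hidden or, when mainly lighter drinkers abstain, reversed. When heavier drinkers abstain, the sign stays right. All sizes rest on assumed abstinence rates, distributions and selection. The assumed arm differences, h = .42 to .61, sit close to the prior marijuana effects, which concern a different substance and comparator. The documents do not support a claim that abstainers will be dropped or that reversal is likely. The change should be made, because effect sizes are this trial's main product and the correction is cheap.

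**What to change.** 1. **Latency.** Define it as time to first use from a stated origin (baseline), censored at the end of the observed window, and analyse it by log-rank test or Cox model instead of growth modeling. The scheduled visits nearly allow continuous observation: week 13 is day 91, and the week 25 window runs from day 85 (175 − 90) to day 175. State how a missed or late 3-month visit, which leaves a gap, is handled.
2. **Consumption.** Base the Aim 2 comparison on variables defined for every assessed teen: use days or days abstinent. Total drinks over 90 days, with abstainers as 0, is an option.
3. **Drinks per drinking day.** Report it descriptively among drinkers, with the number of drinkers in each arm, or use a two-part model (any drinking, then amount). State that it is never imputed for a teen known to be abstinent, and that the same applies at baseline to teens who use only other substances.

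The cost is revised wording and a little more analysis. The TLFB already holds the data. Total drinks, if chosen, mixes frequency with quantity and is skewed with many zeros, which is awkward for a growth model with about 80 teens; use days avoids the first of these problems.
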